Visit 1: Subjects seen approximately 1 week (+/- 4days) after their quit date to assess adverse effects and progress in smoking cessation. At this visit, the nurse administers behavioral counseling (35 minutes) and assesses medication usage. The study coordinator will administer all assessments.

1. Vital signs and weight
2. Exhaled CO measurement
3. Nicotine Use Survey
4. Questionnaires: MNWS
5. Adverse Effects Inhaler & Adverse Events
6. Concomitant Medication
7. Inhaler usage: We will collect used cartridges from patient and review diary of inhaler usage.
8. Counseling: The second counseling session is scheduled 1 week after the quit date. The primary focus of this session will be to assess reactions to the initial session, smoking status, and the effectiveness of the intervention, and to discuss strategies to deal with smoking urges and tobacco withdrawal symptoms. Subsequent sessions will focus on achieving or maintaining abstinence, increasing self-efficacy, skills training (depending on the patient's smoking status), and providing support.

This visit will take 45 minutes.

Visits 2 (2 weeks after the quit date +/- 4 days). The following items will be assessed by research nurse.

1. Vital signs and weight
2. Exhaled CO measurement
3. Maternal Blood draw (15 cc) If possible, this blood draw will be incorporated with other routine prenatal blood draws. Will collect urine as backup.
4. Nicotine Use Survey
5. Questionnaires: MNWS, PHQ
6. Adverse Effects Inhaler & Adverse Events
7. Concomitant Medication
8. Inhaler usage: We will collect used cartridges from patient and review diary of inhaler usage.
9. Dispensement: We will dispense a 2 week supply of study medication, if needed.
10. Counseling (10 Minutes): Counseling will focus on achieving or maintaining abstinence (set another quit date if necessary), increasing self-efficacy, skills training (depending on the patient's smoking status), and providing social support, and using inhaler to combat urges to smoke.

This visit will take 45 minutes. After the session the nurse will send the two maternal serum samples for cotinine analyses. If the visit 2 sample exceeds that of baseline by 40%, the study nurse will call the patient and advise a decrease in inhaler dosage that will be recommended by [name].

Visit 3 (3 weeks after the quit date +/- 4 days). The following items will be assessed by research nurse.

1. Vital signs and weight
2. Exhaled CO measurement
3. Nicotine Use Survey

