4. Assignment: To examine whether the blinding was successful, subjects will be asked which treatment they think they received (active or placebo inhaler).
5. Adverse Effects Inhaler & Adverse Events
6. Concomitant Medication

Nicotine Replacement for Smoking Cessation during Pregnancy

7. MNWS Questionnaire
8. Inhaler usage: We will collect used cartridges from patient and review diary of inhaler useage.
9. Counseling (10 Minutes): Counseling will focus on achieving or maintaining abstinence (set another quit date if necessary), increasing self-efficacy, skills training (depending on the patient's smoking status), and providing social support, and using inhaler to combat urges to smoke).

This visit will take 45 minutes.

Visit 4 (4 weeks after the quit date +/- 4 days). The following items will be assessed by research nurse.

1. Vital signs and weight
2. Exhaled CO measurement
3. Nicotine Use Survey
4. Questionnaires: MNWS
5. Adverse Effects Inhaler & Adverse Events
6. Concomitant Medication
7. Inhaler usage: We will collect used cartridges from patient and review diary of inhaler useage.
8. Dispensement: We will dispense a 2 week supply of study medication, if needed.
9. Counseling (10 Minutes): Counseling will focus on achieving or maintaining abstinence (set another quit date if necessary), increasing self-efficacy, skills training (depending on the patient's smoking status), and providing social support, and using inhaler to combat urges to smoke).

This visit will take 45 minutes.

Visit 5 (6 weeks after the quit date +/-10days). The following items will be assessed by research nurse.

1. Vital signs and weight
2. Exhaled CO measurement
3. Nicotine Use Survey
4. Questionnaires: MNWS, PHQ
5. Adverse Effects Inhaler & Adverse Events
6. Concomitant Medication
7. Inhaler usage: We will collect used cartridges from patient and review diary of inhaler useage.
8. Taper: (Discuss scheduled taper with goal of being off medication by 6 weeks for subjects who are abstinent from cigarette smoking (no smoking last 7 days confirmed with exhaled CO)
9. Maternal Blood draw (15cc). If possible, this blood draw will be incorporated with other routine prenatal blood draws. Will collect urine as backup.

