10. Counseling (10 Minutes): Counseling will focus on achieving or maintaining abstinence (set another quit date if necessary), increasing self-efficacy, skills training (depending on the patient's smoking status), and providing social support, and using inhaler to combat urges to smoke).
11. Serum will be sent for cotinine analysis only if the nurse identifies that the subject has significantly changed her smoking and/or inhaler use patterns (see DSMP for cotinine monitoring).

This visit will take 45 minutes.

Visit 6 (32-34 weeks gestation). The following items will be assessed by research nurse.

1. Vital signs and weight
2. Exhaled CO measurement

Nicotine Replacement for Smoking Cessation during Pregnancy

3. Nicotine Use Survey
4. Questionnaires: MNWS, PHQ
5. Adverse Effects Inhaler & Adverse Events
6. Concomitant Medication
7. Inhaler usage: We will collect used cartridges from patient and review diary of inhaler usage.
8. Maternal Blood Draw (15 cc) If possible, this blood draw will be incorporated with other routine prenatal blood draws. Will collect urine, if necessary.
9. Counseling (10 Minutes): Counseling will focus on achieving or maintaining abstinence (set another quit date if necessary), increasing self-efficacy, skills training (depending on the patient's smoking status), and providing social support, and using inhaler to combat urges to smoke).
10. Serum will be sent for cotinine analysis only if the nurse identifies that the subject has significantly changed her smoking and/or inhaler use patterns (see DSMP for cotinine monitoring).

This visit will take 45 minutes.

Birth outcomes: the research nurse or study coordinator will collect birth outcomes by chart review. Permission to conduct chart review for labor and delivery records will be included in the informed consent form. Information to be collected includes: Apgar scores, birth weight, infant sex, gestational age, head circumference, NICU admission, and infant length of stay. Other rare events associated with tobacco use during pregnancy and maternal medical conditions will also be recorded. Time to collect birth outcomes is estimated at 30 minutes.

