Describe length of subject's participation in the study including number of visits, frequency of visits, and length of visits:

The subject will be in the study from the time of enrollment (13-26 weeks gestation) until 6 months after delivery. Each subject will have 10 visits. The screen and baseline visit are each 1.5 hours long. The remaining visits are approximately 45 minutes long.

Methods of Data Collection and Types of Data to be collected (may refer to attached surveys/ forms etc.)
See Attached surveys

Method(s) of data analysis:

Specific Aim 1: To compare the efficacy in pregnant smokers of the nicotine inhaler or matching placebo for smoking cessation and reduction in pregnant smokers We will first examine variation in the main outcome (7 day PPA rates at 32-34 weeks gestation) by treatment site using the intraclass correlation coefficient. If there is a difference by site, it will be used as a nesting factor in a generalized estimating equations logistic model. At the end of patient follow-up, the difference in the proportion of subjects who successfully quit smoking will be calculated along with a 95% confidence interval for the “true” difference between treatment groups. To evaluate whether randomization was effective, summary statistics for patient characteristics in the two study arms will be compared. If there is an imbalance in patient characteristics, statistical adjustment will be used to ensure that the initial results were not biased by those imbalances.

We will use a linear mixed model to evaluate the effects of the nicotine inhaler on smoking reduction or exhaled CO from baseline first to 6 weeks and then to 32 weeks gestation. Prior to these analyses, the distribution of the dependent variables, number of CPD (and exhaled CO), will be examined for normality and outliers and transformations will be performed if necessary. Treatment group and visit will be fixed factors and the intercept will be random. The model will also include a treatment-by-time interaction to test whether, over time, the number of CPD changes differentially by treatment group.

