Specific Aim 2.a: To compare effects of the nicotine inhaler with placebo on overall nicotine exposure (i.e., measured as serum cotinine), and birth outcomes [i.e., birth weight, gestational age, % of subjects who deliver a LBW (<2500 g) or preterm (<37 wk gestation) infant]. We will use a linear mixed model (see above) to determine whether cotinine concentration changes differentially over time by treatment group.

Specific Aim 2.b: Birth Outcomes. Mean birth weight will be compared for treatment groups using a two-sample t-test, or analysis of covariance if necessary to adjust for imbalances in patient characteristics. We will also compare the percentage of subjects in each group who deliver an infant of LBW (1500-2500 g) or preterm delivery using chi square or logistical regression.

Specific Aim 3: To determine which subjects benefit most from NRT, we will use logistic regression to examine the following predictors of treatment response (i.e., smoking cessation at 6 or 32 wks

Nicotine Replacement for Smoking Cessation during Pregnancy

gestation): pretreatment CPD, FTND score, perceived stress, motivation to quit, self-efficacy, treatment group, and the interaction of treatment group and the other independent (i.e., potential moderator) variables. **Analyses:** First, we will use a stepwise procedure to choose predictor variables and interaction terms that are significant ($\alpha=0.05$). A significant interaction between treatment group and other variables (e.g., pretreatment CPD) implies that the regression coefficients for this variable are not homogeneous with respect to the efficacy of the medication. The Johnson-Neyman procedure [79], which yields values of the continuous moderator variable at which the treatment groups differ significantly on the dependent variable, will be used to determine the “break point” nicotine inhaler efficacy. In our completed study[1], the effect of nicotine gum appeared to depend on CPD during the pretreatment period. For light smokers, the cessation rates were 18% and 21% for the control and nicotine groups, respectively, while for heavy smokers the rates were 0% and 15%, respectively. Since a similar effect in a sample of 150 women would provide power=0.80, using a two-sided $\alpha=0.05$, our proposed sample of 360 pregnant smokers will provide more than adequate power to detect the effect.

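### The mixed model for cigarettes per day, exhaled CO and cotinine names only a random intercept; if correlation between visits falls with time, long-interval contrasts get standard errors that are too small

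*Combined protocol and SAP*

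**What the plan says.** Under Method(s) of data analysis, Specific Aim 1, CPD and exhaled CO are analysed with a linear mixed model "from baseline first to 6 weeks and then to 32 weeks gestation". The covariance specification is one clause: "Treatment group and visit will be fixed factors and the intercept will be random". The test is then named: "The model will also include a treatment-by-time interaction to test whether, over time, the number of CPD changes differentially by treatment group". Normality and outliers are to be checked, with transformation if needed. No random slope, residual covariance structure or robust standard error is mentioned.

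Specific Aim 2.a carries the model to cotinine: "We will use a linear mixed model (see above) to determine whether cotinine concentration changes differentially over time by treatment group".

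The study timeline puts baseline about a week before the quit date. Visits 1 to 4 follow at weeks 1, 2, 3 and 4, and Visit 5 at week 6. The visit description then fixes Visit 6 by gestation, at 32-34 weeks. CPD and CO are collected at all of these visits. Cotinine is scheduled at four: baseline and Visits 2, 5 and 6.

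**The concern.** A random intercept with independent, equal-variance residuals implies one variance and one correlation for all pairs of visits. Here the early visits are one or two weeks apart, while baseline and Visit 6 are separated by months, a quit attempt and the end of treatment. If measurements on the same woman agree less as the gap widens, the model applies the average agreement of mostly close visits to its longest contrast, and the interval comes out too narrow. Transformation addresses the shape of the distribution, not the correlation over time.

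Reduction in CPD is part of Hypothesis 1, and lower cotinine is Hypothesis 2a, which Aim 2 treats as a safety measure. An interval that is too narrow would overstate evidence that the inhaler reduces smoking or nicotine exposure.

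**Working it through.** **The plan's own figures.** There is nothing to reproduce. The only variability figure for these outcomes is the SD of 360 for cotinine reduction in the Aim 2 sample size. It describes one change score and gives no correlation between visits. The calculation below therefore rests on assumed correlations.

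**Visit times.** In weeks from the quit date: -1, 1, 2, 3, 4, 6 and Visit 6. Entry is at 13-26 weeks gestation, so Visit 6 falls about 6 (32 - 26) to 21 (34 - 13) weeks after entry. Week 13 is taken as a central value. The cotinine times are -1, 2, 6 and 13.

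**Formula.** With complete data, the estimated difference in change between arms is the same under either covariance; only its standard error differs. Let D(i,j) = Var(Yi - Yj) within a woman. The random-intercept model estimates one residual variance, equal to the average of D(i,j)/2 over all visit pairs, and uses it for every contrast. Hence

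- r = model SE / true SE = sqrt(mean D / D(baseline, Visit 6))
- type I error = 2 × (1 - Φ(1.96 r))

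**Assumed correlation.** φ^lag with φ = 0.90 or 0.95 per week and equal variances, so D = 2(1 - φ^lag) in units of the variance. A component shared by all visits cancels from D, so adding one does not change r. Measurement noise with share m changes the correlation to (1 - m)φ^lag.

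**CPD/CO, seven visits.** The 21 visit pairs have a mean lag of 108/21 = 5.1 weeks; the contrast of interest has a lag of 14 weeks.

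- φ = 0.90: mean D = 0.749; D(baseline, Visit 6) = 2(1 - 0.229) = 1.543; r = sqrt(0.749/1.543) = 0.70; type I error 17%.
- φ = 0.95: mean D = 0.435; D(baseline, Visit 6) = 1.025; r = 0.65; type I error 20%.
- With m = 10-30%: r = 0.73-0.83; type I error 10-16%.

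**Cotinine, four visits.** Lags are 3, 7, 14, 4, 11 and 7 weeks.

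- φ = 0.90: mean D = 1.039; r = sqrt(1.039/1.543) = 0.82; type I error 11%.
- φ = 0.95: mean D = 0.625; r = sqrt(0.625/1.025) = 0.78; type I error 13%.
- With m = 10-30%: r = 0.82-0.89; type I error 8-11%.

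**Change to week 6.** For CPD/CO, if all seven visits share one model, r = 0.85 without noise (type I error about 10%). A separate model ending at week 6 gives r = 0.68-0.71 (17-18%). For cotinine in the four-visit model, r is 1.00-1.02 and the test is close to nominal.

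**The test the plan names.** Simulating the overall treatment-by-visit test under the same assumptions, with and without noise, gives rejection rates of about 6-10% for CPD/CO and 5-7% for cotinine.

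**Check by model fitting.** Sixty random-intercept fits were run on simulated data with N = 180 and correlation 0.9 × 2^(-lag/8). The mean model SE was 0.132 against a true 0.180 (ratio 0.73), and 13% of runs were falsely significant; the formula predicts 15%.

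**Patterns that behave differently.**

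- Truly equal correlation: r = 1.00.
- Only two time points in the model: r = 1.00.
- Correlation 0.6 between baseline and Visit 6, 0.3 between baseline and the other visits, 0.5 among post-quit visits: mean D = 1.086; D(baseline, Visit 6) = 0.80; r = 1.16; type I error 2%.

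**The case against.** The strongest objection is that the understatement is conditional. A reader might infer that these standard errors will certainly be too small. The documents do not support that: they contain no visit correlations or visit-specific variances, and they leave the residual covariance unstated rather than declaring it independent. The direction can reverse. Women still smoking at Visit 5 stop medication and quitters taper, so relapse could bring Visit 6 back towards baseline. This stands, and it limits the claim to a conditional one. It does not rescue the specification, because in that case too the standard error is wrong, only in the other direction.

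Second, a reader might attach the 17-20% to the planned test. It belongs to a single baseline-to-Visit 6 contrast. The treatment-by-time interaction that the plan names is only mildly affected. This stands.

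Third, the phrase about change first to 6 weeks and then to 32 weeks could mean models with few time points, and with two the problem vanishes. That is possible. But visit is a factor, the text speaks of change over time, and CPD and CO are recorded at every visit, so a model across all visits is the more natural reading.

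Fourth, cotinine should not be given the CPD/CO figures. It has four scheduled values, and the Visit 5 and 6 descriptions send serum for assay only if smoking or inhaler use has changed, while the study timeline lists cotinine there without that condition. Its error is smaller, and its data structure is less certain.

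**Conclusion.** The point holds in conditional form. Fitted as written, the model imposes equal variance and equal correlation on unequally spaced visits. Under decay of 0.90-0.95 per week, Visit 6 near week 13, equal variances and complete data, the baseline-to-Visit 6 standard error is 0.65-0.70 of true for CPD/CO and 0.78-0.82 for cotinine. Measurement noise of 10-30% moves these to 0.73-0.83 and 0.82-0.89. The named interaction test is inflated modestly. None of these sizes can be read from the documents.

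A reader might also infer that the trial's main result is at risk. It is not: the main outcome is 7-day abstinence at 32-34 weeks, analysed separately, and neither it nor its sample size depends on this model. The analyses affected are secondary. The change is worth making because it removes an unverified assumption at almost no cost.

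**What to change.** In Method(s) of data analysis, Specific Aim 1, and by reference Specific Aim 2.a:

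- Replace the random-intercept-only specification with an unstructured within-woman covariance over visits, fitted by REML with Kenward-Roger degrees of freedom. It replaces the random intercept rather than being added to it.
- If that model does not converge, keep the random-intercept model and use robust (sandwich) standard errors.
- Keep the treatment-by-time test. Also report the treatment difference in change from baseline at 6 weeks and at 32-34 weeks, each with a 95% confidence interval.
- State which visits enter each model.

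The cost is a sentence or two of text, more covariance parameters (7 × 8/2 = 28 for seven visits, 4 × 5/2 = 10 for four, with 360 women planned) and possibly wider intervals. No visit, assay or sample size changes.

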Evidence that these biomarkers are mediators of pregnancy outcomes that are affected by smoking has important implications for other pharmacotherapy studies in pregnant smokers by providing surrogate measures of potential risk [46] or in studies of reduced-exposure products (e.g., e-cigarettes, smokeless tobacco) that may be used by pregnant women. Since the FDA has recently been authorized to regulate tobacco products [56] there is likely to be heightened interest in biomarkers of tobacco product risk, particularly in vulnerable populations.

3. Hypotheses, aims and objectives:

Hypothesis 1:

We hypothesize that the nicotine inhaler compared to placebo inhaler will double the 7-day point prevalence abstinence rates (confirmed by exhaled CO) at 32-34 weeks gestation and will reduce the number of cigarettes smoked per day (CPD).

Aims / objectives 1:

To examine the efficacy of the nicotine inhaler compared to a matched placebo for smoking cessation and reduction among pregnant smokers.

Hypothesis 2:

- a) The nicotine inhaler will yield lower cotinine concentrations than placebo at 32-34 weeks gestation.
- b) Infants born to mothers in the NRT group will have higher birth weights and greater gestational age than infants born to mothers randomized to placebo. 2c) Fewer nicotine-treated subjects will deliver a low birth weight (<2500 grams) or a preterm (<37 weeks) infant than those in the placebo group.

Aim/Objective 2:

To compare the nicotine inhaler with placebo on safety measures which include a) overall nicotine exposure (i.e., serum cotinine) and b) birth outcomes (i.e., birth weight and gestational age).

Hypothesis 3: Pregnant women who are heavier smokers (i.e., ≥ 10 cigarettes/day) will be less able to quit with behavioral treatment alone than lighter smokers and the inhaler will increase cigarette abstinence more in heavier smokers.

Aim/Objective 3: To identify factors that determine which women benefit most from the use of nicotine inhaler for smoking cessation during pregnancy

Hypothesis 4: We hypothesize that birth weight will be negatively correlated with CPD and exhaled CO at the end of pregnancy, and that smoking cessation or reduction in the third trimester will explain the effect of treatment group on birth weight. We will also explore the interrelations among birth outcomes, tobacco exposure, and other promising biomarkers.

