- ii. enrolled subjects met eligibility criteria and
- iii. all study procedures are completed as outlined in the study protocol.
- c. Verification of protocol adherence and verification that all deviations from the protocol are documented with an explanation of circumstances.
- d. Verification that subjects failing to complete the study and the reason for each failure are noted
- e. Performance of a serious adverse event review; with emphasis on the proper follow-up and reporting of adverse events
- f. Verification of investigational product accountability (review drug handling, drug accountability, drug temperature logs, review each chart for physician sign off).
- g. Performance of a review of the study regulatory file
- h. Performance of a review of the data and safety monitoring plan meeting minutes/notes.

Timetable:

Expected Start Date: **12/1/10**

Timeline of Study Procedures (including time to administer questionnaires and other procedures):

Assessment	Pt time (min)	Screen	Baseline (wk -1 before QD)	Visit 1 (wk 1 after QD)	Visit 2 (wk 2 after QD)	Visit 3 (wk 3 after QD)	Visit 4 (wk 4 after QD)	Visit 5 (wk 6 after QD)	Visit 6 (32-36 wk GA)	Visits 7** & 8 (1 & appox. 6 months postpartum)
Visit window				+/- 4	+/- 4	+/- 4	+/- 4	+/- 10	N/A	V.7(+/- 7), V.8(+/- 14)
Demographics	2	X								
Smoking and FTND	10	X								
Medical Screen	20	X								
Social Support and Self-Efficacy Questionnaires	5	X								
PRIME-MD PHQ	2	X	X		X			X	X	
Vital signs & Weight	5	X	X	X	X	X	X	X	X	
Nicotine Use Survey	1	X	X	X	X	X	X	X	X	X
Cotinine, Biomarkers, and hydroxycotinine/cotinine ratio	5		X		X			X	X	
Carbon monoxide	2	X	X	X	X	X	X	X	X	X
Urine sample as backup	5		X		X			X	X	
Smoking cessation counseling ^a	10		X ^a	X ^a	X	X	X	X	X	
MNWS	2		X	X	X	X	X	X		

Nicotine Replacement for Smoking Cessation during Pregnancy

Adverse Effects	2		X	X	X	X	X	X	X	
Concomitant Medication	2	X	X	X	X	X	X	X	X	
Medication Dispensement	5		X		X		X			
Inhaler Usage	2			X	X	X	X	X	X	
Assignment Question	1					X				
Birth Outcomes*	30									

*Information obtained by chart review by study personnel; ** phone interview; GA = Gestational Age; QD=Quit Date; ^a Counseling will be approximately 35 minutes for the first 2 sessions, and 10 minutes for subsequent sessions; ^b Proposed medication dispensing times. If the subject misses a visit, drug may be dispensed at a subsequent visit.

Timeline of Performance Goals for the entire study:

Activity	Year 1	Year 2	Year 3	Year 4	Year 5

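### Hypothesis 2a concerns cotinine at 32-34 weeks, but its only named test is a 3-df treatment-by-visit interaction, which a difference already gone by then could make significant

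*Combined protocol and SAP*

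**What the plan says.** Hypothesis 2a (section 3, Hypotheses, aims and objectives) is directional and fixed in time: "The nicotine inhaler will yield lower cotinine concentrations than placebo at 32-34 weeks gestation".

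Its analysis is under Method(s) of data analysis, Specific Aim 2.a. A linear mixed model, by reference to the one in Specific Aim 1, is to be used "to determine whether cotinine concentration changes differentially over time by treatment group". No time window, visit-specific contrast or confidence interval is given.

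The Aim 1 model is described as follows: "Treatment group and visit will be fixed factors and the intercept will be random". The test named there is "The model will also include a treatment-by-time interaction to test whether, over time, the number of CPD changes differentially by treatment group". For cigarettes per day (CPD) and exhaled CO, that paragraph also names two windows, evaluating "smoking reduction or exhaled CO from baseline first to 6 weeks and then to 32 weeks gestation". It does not list the visits in each window.

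The Timeline of Study Procedures has one row, "Cotinine, Biomarkers, and hydroxycotinine/cotinine ratio", marked at baseline and Visits 2, 5 and 6. Under Study design and the pharmacotherapy overview, drug is given for 6 weeks and then tapered over 6 weeks; women still smoking at Visit 5 come off it.

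**The concern.** With visit as a categorical factor, the interaction asks whether the difference between arms is the same at every visit. It rejects for any departure, in either direction, at any visit. Hypothesis 2a asks something narrower: whether cotinine is lower on the inhaler at the last antenatal visit.

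The two questions separate in the situation this design makes plausible. Cotinine is a metabolite of nicotine, so it reflects both smoking and inhaler use at Visits 2 and 5. By 32-34 weeks many women will have tapered or stopped the drug. A difference present during treatment and absent at Visit 6 is a real treatment-by-visit interaction, but it is not evidence for Hypothesis 2a.

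Cotinine is one of the safety measures in Aim 2. A significant interaction could be read as lower exposure late in pregnancy when exposure at that point is equal or even higher.

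**Working it through.** **The plan's own figure.** Sample size and justification, Aim 2, gives 226 subjects in total for a 100 ng/mL difference in cotinine reduction, SD 360, power 0.80, two-sided α 0.05. The usual formula gives n per arm = 2 × (1.960 + 0.842)² × (360/100)² = 203.4, so 204 per arm or 408 in total. The 226 does not reproduce: power is 0.55 with 226 in total and 0.75 with the planned 360. That is a separate matter. Only the 100 and the 360 are used below.

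**Inputs.** From the plan: 180 per arm, difference 100 ng/mL, SD 360, cotinine at baseline, V2, V5 and V6, and 75% data collection in the completed trial (Incentives). Assumed: 360 is the SD of change, and the correlation is compound symmetric, as a random intercept implies. Then σe² = 360²/2 = 64,800. The same value results if 360 is the SD of a single measurement and the between-visit correlation is 0.5.

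**Formula.** With d_t the true difference between arms at visit t and T visits, the interaction test has T − 1 df and noncentrality λ = (n/2) × Σ(d_t − d̄)² / σe².

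**Cotinine, difference at V2 and V5 only.** For d = 0, 100, 100, 0: d̄ = 50, Σ(d_t − d̄)² = 10,000, and λ = 90 × 10,000 / 64,800 = 13.9 on 3 df.

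| Difference at V2 and V5 (zero at V6) | n per arm | λ | P(interaction significant) |
|---|---|---|---|
| 100 | 180 | 13.9 | 0.89 |
| 75 | 180 | 7.8 | 0.64 |
| 50 | 180 | 3.5 | 0.31 |
| 100 | 135 (75% of 180) | 10.4 | 0.78 |

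The V6-minus-baseline contrast rejects with probability 0.05 in every row, because the effect it tests is zero. In 300 simulated trials of the first row, fitted with the random-intercept model, the interaction rejected in 0.90 and the V6 contrast in 0.04.

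**Direction.** λ depends on squared deviations, so changing the sign of every d_t changes nothing. If the inhaler arm is lower by 100 at V2 and V5 but higher by 50 at V6, then d̄ = −37.5, Σ(d_t − d̄)² = 16,875 and λ = 23.4. The interaction is then significant with probability 0.99, although Hypothesis 2a is false.

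**CPD and CO.** The documents give no CPD standard deviation, so differences are in units of the SD of change (σe² = 0.5).
- If the second window contains only baseline and V6, the interaction is the V6 contrast and rejects at 0.05 when nothing is left at V6.
- If it contains baseline and V1 to V6, with a difference at V1-V5 and none at V6, the 6-df test rejects with probability 0.18 at 0.1 SD, 0.66 at 0.2 SD and 0.97 at 0.3 SD.

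**Time as a linear trend.** Under the same fading pattern, rejection is only about 0.13 to 0.31. Naming visit as a fixed factor argues against that reading.

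**The case against.** The best defence concerns CPD and CO. The plan names two windows, and if the second compares baseline with 32 weeks the difficulty vanishes. Hypothesis 1 attaches 32-34 weeks to abstinence; its CPD clause has no clear time point, so a reduction seen only on treatment would be consistent with it. Both points stand. A reader might infer that the CPD conclusion is exposed in the same way as cotinine, but the documents do not support that.

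A second objection is that cotinine on the inhaler is unlikely to exceed cotinine on placebo. The background puts inhaler exposure at about 60% of that with smoking, the pilot reports 66% replacement, and the earlier gum trial found a greater cotinine reduction on nicotine. This is fair: the documents do not support an inference that the inhaler raises cotinine. It does not rescue the test, which reacts equally to a lower value that fades.

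Third, the fitted model yields visit-specific estimates, nothing says the interaction alone will be reported, and the sample-size text speaks of a single between-group difference in reduction. That is so, and an analyst could extract the right contrast. The plan nevertheless names one test for this hypothesis, and it is a different one.

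Finally, the main outcome, 7-day abstinence at 32-34 weeks, has its own group difference with a 95% CI and is unaffected.

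**Conclusion.** The point holds for cotinine. The named test does not answer Hypothesis 2a, and a fading on-treatment difference could make it significant with probability 0.31 to 0.89 for differences of 50 to 100 ng/mL at 180 per arm. The word is could: the result depends on the size of the on-treatment difference and on its having gone by Visit 6, neither of which is known. The figures rest on SD 360 as the SD of change, compound symmetry, and complete data at all four visits except in the 75% case.

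The last assumption needs checking, because the text for Visits 5 and 6 says "Serum will be sent for cotinine analysis only if the nurse identifies that the subject has significantly changed her smoking" or inhaler use, whereas the schedule lists cotinine at those visits without condition. Those places should be reconciled, but the mismatch between test and hypothesis does not depend on it.

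For CPD and CO the finding is conditional: the problem arises only if the second window includes intermediate visits.

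**What to change.** Under Specific Aim 2.a, name the baseline-adjusted treatment difference in cotinine at 32-34 weeks (Visit 6), estimated from the same mixed model with a 95% CI, as the single 1-df test of Hypothesis 2a.

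Under Specific Aim 1, state the time point of the CPD hypothesis, and give the treatment contrasts for baseline to 6 weeks and baseline to 32-34 weeks as the two window results for CPD and CO. Keep the treatment-by-visit interaction as supportive or descriptive.

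This takes a few sentences of analysis text and no new data, visits or subjects. The cost in power is small. For a 100 ng/mL difference sustained from V2 to V6, the unadjusted change contrast has power 0.75 (standard error 360 × √(2/180) = 37.9; Φ(100/37.9 − 1.96) = Φ(0.68)), against 0.78 for the interaction. Baseline adjustment should recover this: with correlation ρ it multiplies the variance of the change contrast by (1 + ρ)/2. At an assumed ρ of 0.5 that gives a standard error of 37.9 × √0.75 = 32.9 and power Φ(100/32.9 − 1.96) = Φ(1.08) = 0.86.
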